## PROTOCOL AMENDMENTS

Protocol Version	Issue Date
Original Protocol	06 July 2017
Amendment 1	29 August 2017
Amendment 1 / Finland-1	29 September 2017
Amendment 1 / UK-1	03 October 2017
Amendment 2	08 January 2018
Amendment 3	14 November 2018
Amendment 4	18 April 2019

*Amendments below are listed beginning with the most recent amendment.*

### **Amendment 4** (Issued date: 18 April 2019)

**The overall reason for the amendment:** This protocol amendment is made to reduce the overall number of RSV-seropositive toddlers in the study from 48 to 36. The rationale for this reduction is as follows:

As of 18 April 2019, 35 seropositive toddlers have been enrolled in the current study (VAC18194RSV2001). The IDMC have reviewed available safety and immunogenicity data from the planned interim analysis, unblinded at the group level, when at least 24 toddlers had reached Day 29 or discontinued earlier. As enrollment was staggered over time, the analysis contained solicited and unsolicited AE data post-Dose 1 from 32 toddlers, of whom 30 toddlers already had post-Dose 2 data and 28 were in follow-up.

The IDMC concluded that the safety profile was acceptable and supported progression to the next study (VAC18194RSV2002) in RSV-seronegative toddlers aged 12 to 24 months in which subjects will receive half the dose of Ad26.RSV.preF used in the current study (ie,  $2.5 \times 10^{10}$  vp). In addition, blinded safety review by the sponsor of additional data since the IDMC review has not revealed any safety concerns. Study VAC18194RSV2002 has already been initiated; as of 18 April 2019, 6 seronegative toddlers have been enrolled and have received their first vaccination.

The reduction in the number of seropositive toddlers in the current study is supported by the expectation that there would be no difference in the local and systemic reactogenicity between seropositive and seronegative toddlers. The collection of safety data at the planned dose in seronegative toddlers in study VAC18194RSV2002 will therefore add to the overall safety database in this age group as planned. Furthermore, as RSV-seropositive toddlers are at limited to no risk of severe RSV disease, there would be limited value in continuation of the study.

*The table below gives an overview of the rationale for each change and all affected sections*

**Rationale:** As indicated above, the number of RSV-seropositive toddlers in this study is reduced from 48 to 36.

*Synopsis: Overview of Study Design; Sample Size Determination*

*3.1 Overview of Study Design*

*11.2 Sample Size Determination*

### **Amendment 3** (Issued date: 14 November 2018)

**The overall reason for the amendment:** To potentially aid recruitment in the current study, this protocol amendment is made to allow enrollment of RSV seropositive toddlers who have been screened for a different clinical study of the sponsor (ie, VAC18194RSV2002) if RSV seropositivity was determined using the RSV EIA or virus neutralization assay.

Other updates and clarifications are made as specified below.

---

*The table below gives an overview of the rationale for each change and all affected sections*

---

**Rationale:** Added clarification that RSV-seropositive subjects can be enrolled if their serostatus has been confirmed by either RSV EIA or virus neutralization assay from a different study of the sponsor.

---

*Synopsis: Other Evaluations – RSV Infection*

*Time and Events Schedule*

*4.1.2 Inclusion Criteria – Pediatric Subjects*

*9.1.4.1 Screening Phase: Days –42 to 1*

*9.2.2 Other Evaluations – RSV Infection*

---

**Rationale:** Change of EIA cut-off criterion for seropositivity to titers >10 EIA units.

---

*Synopsis: Other Evaluations – RSV Infection*

*9.2.2 Other Evaluations – RSV Infection*

---

**Rationale:** Update of preclinical information.

---

*1.1 Background*

---

**Rationale:** Update of clinical information.

---

*1.1 Background*

---

**Rationale:** Clarification of wording of Exclusion Criterion 23 for pediatric subjects.

---

*4.2.2 Exclusion Criteria – Pediatric Subjects*

---

**Rationale:** Clarification of the exclusion criterion for known allergies at screening refers to vaccines or vaccine components, but not to egg allergies.

---

*4.2.2 Exclusion Criteria – Pediatric Subjects*

---

**Rationale:** Clarification that the exclusion criterion for urticaria, eczema and atopic dermatitis relates to a moderate to severe history of these illnesses.

---

*4.2.2 Exclusion Criteria – Pediatric Subjects*

---

**Rationale:** Clarification that telephone calls to subjects for RTI monitoring after the first dose will be made during both the active and safety follow-up phases.

---

*Synopsis: Overview of Study Design*

*Time and Events Schedule*

*3.1 Overview of Study Design*

*9.1.4.3 Safety Follow-up Phase*

---

**Rationale:** Clarification that during each 28-day post-vaccination period, all RTIs will be reported and that during the RSV season, but outside the 28-day post-vaccination period, only RTIs for which a combination of respiratory symptoms develop, will be reported.

---

*Synopsis: RTI – Procedures Specific to Cohort 1; Other Evaluations – RSV Infection; Safety Evaluations*

*Time and Events Schedule*

*3.2 RTI – Procedures Specific to Cohort 1*

*3.4.5 Overall Benefit/Risk Assessment*

*9.2.2 Other Evaluations – RSV Infection*

---

**Rationale:** Clarification that in the event of an ongoing AE or other situation precluding subject vaccination within 10 days, subjects may be vaccinated beyond the 10-day window at the discretion of the sponsor.

---

*Time and Events Schedule**3.4.5 Overall Benefit/Risk Assessment**9.1.3.2.1 Vaccination (Days 1 and 29)**9.1.4.2.1 Vaccination (Days 1 and 29)**10.3 Contraindications to Vaccination*

**Rationale:** Clarification that any subject who receives study vaccine beyond the Day 29 window specified in the Time and Events Schedule would not be included in the per-protocol immunogenicity analyses.

*11.1 Analysis Sets*

**Rationale:** For operational reasons, removal of the requirement for surveillance of primary care physicians, and/or hospitals' urgent care facilities to monitor for subjects seeking medical attention for an RTI.

*3.4.5 Overall Benefit/Risk Assessment*

**Rationale:** Specification that the 1 year post-first vaccination safety follow-up telephone call should take place within a  $\pm 14$  days visit window.

*Time and Events Schedule**9.1.2 Visit Windows*

**Rationale:** Other minor changes, clarifications and corrections made throughout the protocol.

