### **Second-dose Safety**

Post-second dose 48-hour and 7-day safety assessments will be monitored by the PI(s) and the SRP(s).

Administration of the second dose will also be staggered to allow safety assessments to be made 7 days after the second dose in all 12 adults in Cohort 0 before administering the second dose to seropositive toddlers in Cohort 1. Likewise, safety assessments will be made 7 days after the second dose in the first

a The safety of Ad26.RSV.preF in elderly subjects at  $5 \times 10^{10}$  vp and  $1 \times 10^{11}$  vp will have been established in study VAC18193RSV1003 prior to initiation of the current study; the purpose of dosing Ad26.RSV.preF in Cohort 0 in the current study is as a safety check for the new drug product formulation buffer, and consequently only PI and SRP review of Cohort 0 safety data is planned prior to dosing seropositive toddlers in Cohort 1.

12 seropositive toddlers in Cohort 1 before administering the second dose to the remaining seropositive toddlers in Cohort 1. These safety assessments are described more fully in Section 3.1. In addition, 48-hour safety will be checked after dosing sentinel subjects in both cohorts.

The sponsor will monitor post-vaccination safety on an ongoing basis by reviewing blinded safety data.

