- For those subjects who are unable to continue participation in the study up to Visit 9, but for whom consent is not withdrawn, an exit visit will be conducted as soon as possible
- On Days 3 and 31, a telephone call will *additionally* be made to sentinel subjects in Cohort 0 to collect safety information
- On Days 3 and 31, a telephone call will *additionally* be made to parent(s)/legal guardian(s) of sentinel subjects in Cohort 1 to collect safety information
- If any subject in Cohort 0, or any of the first 12 subjects in Cohort 1 come in earlier than Day 8 for Visit 4 (allowed window is ±2 days), a subsequent phone call will be made at the end of the diary period to collect diary card information recorded between the actual visit and the end of the diary period on Day 8
- Signing of the ICF should be done before any study-related activity
- Systolic and diastolic blood pressure, respiratory rate, heart rate, body temperature
- Respiratory rate, heart rate, body temperature
- For women of childbearing potential only

- l. 0.5 mL of blood for serostatus assessment can be collected at screening by venous blood sample or fingerstick, at the discretion of the investigator. If 0.5 mL is collected at screening, baseline blood draw for immunogenicity should be on Day 1.
- m. Note: RSV-seropositive toddlers may be recruited if RSV seropositivity was assessed via RSV EIA or virus neutralization assay in a different study of the sponsor.
- n. Cohort 0: to include exclusion criteria 1, 4, 8, 9, 10, 11, 15, 16 and 17
- o. Cohort 1: to include exclusion criteria 21, 22, 25, 26, 28, and 32
- p. Blood for cellular immunity will also provide plasma for humoral assessments
- q. Investigator must check for acute illness or body temperature  $\geq 38.0$  °C at the time of vaccination. If before the first vaccination, the subject may be enrolled at a later date if within the screening window (otherwise, rescreening is required), or be withdrawn at the discretion of the investigator and after consultation with the sponsor. If before the second vaccination, the subject may be vaccinated up to, and no later than 10 days after the scheduled vaccination, or be withdrawn at the discretion of the investigator and after consultation with the sponsor. In the event of an ongoing AE or other situation precluding subject vaccination within 10 days, subjects may be vaccinated beyond the 10-day window at the discretion of the sponsor.

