### 11.1. Analysis Sets

The **Full Analysis Set (FA)** includes all subjects who were randomized and received at least one dose of study vaccine, regardless of the occurrence of protocol deviations. Vaccination assignment will follow the as-treated principle. All safety analyses will be based on the FA set. As a sensitivity analysis, key immunogenicity tables will also be based on the FA set.

The **Per-protocol Immunogenicity Set (PPI)** will include all randomized and vaccinated subjects for whom immunogenicity data are available, excluding subjects with major protocol deviations expected to impact the immunogenicity outcomes.

In addition, the following samples will not be included in the PPI set:

- If subjects miss one or more doses, but continue the planned visit schedule, samples taken after the planned but missed dose(s) will not be taken into account;
- For subjects who experience a natural RSV infection (based on RT-PCR, or other sources), samples taken after the natural infection are not be taken into account.
- Any subject who receives study vaccine beyond the Day 29 window specified in the Time and Events Schedule would not be included in the per-protocol immunogenicity analyses.

The analysis of immunogenicity will be based on the PPI set.

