### 2.3.2. Immunogenicity Analysis Set

#### 2.3.2.1. Per Protocol Immunogenicity Population (PPI)

The **Per-protocol Immunogenicity Set (PPI)** will include all randomized and vaccinated subjects for whom immunogenicity data are available, excluding subject samples with major protocol deviations expecting to impact the immunogenicity outcomes.

In addition, the following samples will not be included in the PPI set:

- If subjects miss one or more doses, but continue the planned visit schedule, samples taken after the planned but missed dose(s) will not be taken into account;
- For subjects who experience a natural RSV infection (based on RT-PCR, or other sources), samples taken after the natural infection are not be taken into account.

The analysis of immunogenicity will be based on the PPI set.

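### Protocol 11.1 drops a late-dosed subject's whole immunogenicity record, including samples drawn before the late dose, and the SAP omits the rule

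*Protocol*

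**What the plan says.** Protocol 11.1 bases the immunogenicity analysis on the PPI set, and 11.5 calls it the primary set. After the general definition, 11.1 adds a list that opens "In addition, the following samples will not be included in the PPI set". The first two entries work by sample:

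- After a missed dose, "samples taken after the planned but missed dose(s) will not be taken into account".
- After a natural RSV infection, "samples taken after the natural infection are not be taken into account".

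The third entry works by subject, in the words logged for Amendment 3: "any subject who receives study vaccine beyond the Day 29 window specified in the Time and Events Schedule would not be included". It governs the per-protocol immunogenicity analyses. The Amendment 3 log describes it as a clarification and gives no reason for the change of unit.

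SAP 2.3.2.1 repeats the first two entries and leaves out the third. Its general exclusion is also by sample ("excluding subject samples with major protocol deviations expecting to impact the immunogenicity outcomes"), where the matching Protocol sentence excludes subjects.

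On timing, both Time and Events Schedules and Protocol 9.1.2 give dose 2 a window of ±3 days around Day 29. Footnote q to the schedules allows deferral of up to 10 days for acute illness or fever, and continues: "In the event of an ongoing AE or other situation precluding subject vaccination within 10 days, subjects may be vaccinated beyond the 10-day window". That further deferral is left to the sponsor.

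On sampling, Protocol 9.1.4.2.1 has the Visit 5 blood drawn before dose 2. The Cohort 1 schedule lists cellular blood at baseline and before dose 2, and humoral blood only on Days 57 and 211.

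**The concern.** An injection given late on or after Visit 5 cannot change blood already taken. Removing the whole subject therefore discards valid baseline values and, where Visit 5 blood was drawn on schedule, valid post-dose-1 values. It also treats a late dose more harshly than a missed one, with no stated rationale.

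Two things are at stake. First, Th1/Th2 profiling is a secondary endpoint. In toddlers its scheduled samples all precede dose 2, so the literal rule takes every one of them from the primary immunogenicity set for a late-dosed child. Second, the permitted reasons for deferral include illness, fever and an ongoing adverse event. If such children are removed, the Day 29 summary of the response to dose 1 is conditioned on something that happened after dose 1.

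Because the SAP omits the rule, a programmer working from the SAP and one working from the Protocol would build different PPI sets.

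**Working it through.** **Plan's own figure.** The only sample-size figures are the adverse-event detection probabilities in Protocol 11.2, 1 − (1 − p)^N. For p = 5% and N = 24, 1 − 0.95^24 = 70.8%, printed as 71%. All 28 cells reproduce. They do not bear on the PPI rule, for which the documents give no figure.

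**What each event removes in Cohort 1, on the literal Protocol text:**

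| Sample | Dose 2 missed | Dose 2 late |
|---|---|---|
| Baseline, humoral and cellular | kept | removed |
| Pre-dose 2, humoral and cellular | kept | removed |
| Day 57, humoral | removed | removed |
| Day 211, humoral | removed | removed |

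An early exit after Day 29 collects humoral blood only (Protocol 9.1.4.2.4), so no later cellular sample replaces those lost.

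**Precision.** SAP 6.3.1.1 reports geometric means with a 95% CI computed on the log2 scale. In SD units the half-width is t(0.975, n−1)/√n. For n = 12 this is 2.201/√12 = 0.635, and for n = 11 it is 2.228/√11 = 0.672. Arm sizes are from Protocol Table 5.

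| Arm | n | Half-width (SD units) | Change |
|---|---|---|---|
| Active toddlers | 24 | 0.422 | – |
| | 23 | 0.432 | +2.4% |
| | 22 | 0.443 | +5.0% |
| Placebo toddlers | 12 | 0.635 | – |
| | 11 | 0.672 | +5.7% |
| | 10 | 0.715 | +12.6% |
| Active adults | 8 | 0.836 | – |
| | 7 | 0.925 | +10.6% |
| Placebo adults | 4 | 1.591 | – |
| | 3 | 2.484 | +56% |

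**Number affected (assumed).** At late-dose rates of 5%, 10% and 20%, the expected losses are 1.2, 2.4 and 4.8 of 24 active toddlers, and 0.6, 1.2 and 2.4 of 12 placebo toddlers.

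**Selection (assumed).** Suppose the k late subjects of N differ from the rest by D on the log2 scale. The retained geometric mean then differs from the full-group one by the factor 2^(−kD/N). With D = ±1 (a twofold difference), losing 2 of 24 gives 0.944 or 1.059, and losing 2 of 12 gives 0.891 or 1.122. The documents give neither the size nor the direction of D.

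**Staggering.** Protocol 3.1 requires "safety assessments to be made 7 days after the second dose in all 12 adults in Cohort 0 before administering the second dose" to toddlers, and a second gate holds back the remaining toddlers until the first 12 are reviewed.

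- *Adult gate.* Let the last adult have dose 1 on calendar day 0. On schedule, the 7-day data after dose 2 exist on day 28 + 7 = 35. A toddler first dosed on day 8 has until 8 + 28 + 3 = day 39, so nothing is forced late. If the adult's dose 2 is deferred by 10 days, the data exist on 28 + 10 + 7 = day 45, and that toddler is past ±3.
- *Toddler gate.* Let T be dose 1 of the last of the first 12, r1 and r2 the review times after doses 1 and 2, and d the delay to the last dose 2 in that group. The gate opens at T + 35 + d + r2. The earliest remaining toddler's ±3 window closes at T + 7 + r1 + 28 + 3 = T + 38 + r1. Lateness is forced only if d + (r2 − r1) > 3.

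**The case against.** **The SAP would not apply the rule.** Protocol section 11 leaves detail to the SAP, whose exclusions are by sample, and even the Protocol's list is introduced as a list of samples. This stands in part. The loss follows from the literal Protocol bullet and is not certain in practice. It also means that the documents disagree and need one wording.

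**Subject-level exclusion is normal in a per-protocol set.** The Protocol's general PPI sentence already removes subjects with major deviations. That is fair, but it does not explain why a late dose costs more data than a missed one within one list.

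**The trigger is unclear.** A reader might infer that a toddler dosed on Day 33 is certainly excluded. The ±3 entries support that, but the bullet refers to a schedule whose footnote q has its own 10-day window. On that reading Day 33 stays in, and the staggering example fails, because 8 + 28 + 10 = day 46 falls after day 45. This objection stands.

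**The Visit 5 sample may move with the dose.** A reader might infer that every late-dosed subject has a valid Day 29 sample. The documents do not say whether blood is drawn on schedule when dosing is deferred. If it moves too, it may be outside its own window, and only baseline is clearly recoverable.

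**Staggering.** A reader might infer that the design itself pushes subjects out. On the nominal schedule it does not; it only passes on an earlier delay or a slower second review. A delay caused by another subject is also not selection on the excluded child's health. By Amendment 4, 35 toddlers were enrolled and 30 had post-dose-2 data, so this route is largely past.

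**The data are not discarded.** Late-dosed subjects remain in the FA set. Protocol 11.1 and SAP 2.3.1 commit to repeating key tables on it, although SAP section 6 makes this optional.

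**Conclusion.** The inconsistency is real and worth correcting. Protocol 11.1, read literally, removes samples that the late dose cannot have affected, treats a late dose more severely than a missed one, and differs from SAP 2.3.2.1. The clearest loss is a late-dosed toddler's entire scheduled cellular record in the primary immunogenicity set.

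The size is modest in Cohort 1 for one or two losses per arm: 2% to 5% wider intervals in the active arm and 6% to 13% in the placebo arm. These figures assume complete data otherwise and an unchanged SD. The number of late doses is not given. Bias in the post-dose-1 summary is possible because illness, fever and adverse events are permitted reasons for deferral. It is not demonstrated, since other situations are permitted reasons too and no difference in response is documented. No test, alpha or power is involved.

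**What to change.** Replace the third bullet of Protocol 11.1, and add the same text to SAP 2.3.2.1:

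*If dose 2 is given beyond the Day 29 window, samples drawn after that dose are excluded; the baseline sample is kept, and the pre-dose-2 sample is kept if it was drawn within its scheduled visit window.*

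The condition on the pre-dose-2 sample stops a much later sample from being counted as Day 29. Keeping the term beyond, rather than outside, avoids adding an exclusion for early doses.

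In the same edit, state which window triggers the rule. The ±3 days in the schedules and in 9.1.2 must be reconciled with the 10 days in footnote q.

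The cost is about one sentence in each document, with no new data and no change in conduct. Exclusions at Days 57 and 211 are unchanged from the current Protocol rule. The contributing n will differ by time point, as it already does under the missed-dose and infection rules.

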**Amendment 2** (Issued date: 08 January 2018)**The overall reason for the amendment:**

This amendment is made to increase the number of seropositive toddlers by 12 to generate additional safety data, to specify post-vaccination monitoring time and to correct minor changes, clarifications and corrections made throughout the protocol.

*The table below gives an overview of the rationale for each change and all affected sections*

**Rationale:** To add 12 extra seropositive toddlers to Cohort 1.

*Synopsis**3.1 Overview of Study Design**11.2 Sample Size Determination*

**Rationale:** Removal of Attachment 3 containing information for sites in the United Kingdom (removal already effected via prior separate country-specific amendments: Clinical Trial Protocol Amendment 1 / Finland 1 – 29 September 2017 and Clinical Trial Protocol Amendment 1 / UK 1 – 03 October 2017).

*3.4.2 Potential Benefits**Attachment 3*

**Rationale:** Specification of monitoring time to be a minimum of 30 or 60 minutes post-vaccination in accordance with local approvals (change already effected via prior separate country specific amendment: Clinical Trial Protocol Amendment 1 / Finland 1 – 29 September 2017).

*Synopsis**Time and Events Schedule**3.1 Overview of Study Design**3.4.5 Overall Benefit/Risk Assessment**9.1.3.2.1 Vaccination (Days 1 and 29)**9.1.4.2.1 Vaccination (Days 1 and 29)**9.2.3 Safety Evaluations*

---

**Rationale:** Clarification that a least 5 toddlers in the active group are to have received first dose in a clinic setting and to have completed Visit 3 with no safety concerns before moving to vaccination of study subjects in a non-clinic setting.

---

*Synopsis*

*Time and Events Schedule*

*3.1 Overview of Study Design*

*9.1.4 Screening and Study Visits – Cohort 1 (Seropositive Toddlers)*

---

**Rationale:** Deletion of the wording “In addition, for a selection of tables, tabulations per dose by vaccine will be provided.”, as the per dose analysis will no longer be carried out.

---

*Synopsis*

*11.7 Safety Analysis*

---

**Rationale:** Clarification that the unblinded pharmacist or other qualified individual will have no other study function from randomization onwards

---

*Synopsis*

*3.1 Overview of Study Design*

*5 Study Vaccine Allocation and Blinding*

*6 Dosage and Administration*

*14.3 Storage and Handling*

---

**Rationale:** To specify that the blood volume drawn for serology testing will not exceed 15mL and adjust total blood volume that will be collected.

---

*Time and Events Schedule*

*9.1.1 Overview*

---

**Rationale:** Other minor changes, clarifications and corrections made throughout the protocol.

---

---

**Amendment 1 / UK-1** (Issued date: 03 October 2017)

